8.1. Safety definitions

8.1.1. Definition of an adverse event

An AE is any untoward medical occurrence in a clinical investigation subject, temporally associated with the use of a medicinal product, whether or not considered related to the medicinal product.

An AE can therefore be any unfavourable and unintended sign (including an abnormal laboratory finding), symptom, or disease (new or exacerbated) temporally associated with the use of a medicinal product. For marketed medicinal products, this also includes failure to produce expected benefits (i.e. lack of efficacy), abuse or misuse.

Examples of an AE include:

- Exacerbation of a chronic or intermittent pre-existing condition including either an increase in frequency and/or intensity of the condition.
- New conditions detected or diagnosed after investigational vaccine administration even though they may have been present prior to the start of the study.
- Signs, symptoms, or the clinical sequelae of a suspected interaction.
- Signs, symptoms, or the clinical sequelae of a suspected overdose of either investigational vaccine or a concurrent medication (overdose per se should not be reported as an AE/SAE).
- Signs, symptoms temporally associated with vaccine administration.
- Pre- or post-treatment events that occur as a result of protocol-mandated procedures (i.e. invasive procedures, modification of subject's previous therapeutic regimen).

AEs to be recorded as endpoints (solicited AEs) are described in Section 8.1.3. All other AEs will be recorded as UNSOLICITED AEs.

Examples of an AE DO NOT include:

- Medical or surgical procedures (e.g. endoscopy, appendectomy); the condition that leads to the procedure is an AE/SAE.
- Situations where an untoward medical occurrence did not occur (e.g. social and/or convenience admission to a hospital, admission for routine examination).

- Anticipated day-to-day fluctuations of pre-existing disease(s) or condition(s) present or detected at the start of the study that do not worsen.
- Pre-existing conditions or signs and/or symptoms present in a subject prior to the first study vaccination. These events will be recorded in the medical history section of the eCRF.

8.1.2. Definition of a serious adverse event

A SAE is any untoward medical occurrence that:

- a. Results in death,
- b. Is life-threatening,

Note: The term 'life-threatening' in the definition of 'serious' refers to an event in which the subject was at risk of death at the time of the event. It does not refer to an event, which hypothetically might have caused death, had it been more severe.

- c. Requires hospitalisation or prolongation of existing hospitalisation,

Note: In general, hospitalisation signifies that the subject has been admitted at the hospital or emergency ward for observation and/or treatment that would not have been appropriate in the physician's office or in an out-patient setting. Complications that occur during hospitalisation are also considered AEs. If a complication prolongs hospitalisation or fulfils any other serious criteria, the event will also be considered serious. When in doubt as to whether 'hospitalisation' occurred or was necessary, the AE should be considered serious.

Hospitalisation for elective treatment of a pre-existing condition (known or diagnosed prior to informed consent signature) that did not worsen from baseline is NOT considered an AE.

- d. Results in disability/incapacity, OR

Note: The term disability means a substantial disruption of a person's ability to conduct normal life functions. This definition is not intended to include experiences of relatively minor medical significance such as uncomplicated headache, nausea, vomiting, diarrhoea, influenza like illness, and accidental trauma (e.g. sprained ankle) which may interfere or prevent everyday life functions but do not constitute a substantial disruption.

- e. Is a congenital anomaly/birth defect in the offspring of a study subject.

Medical or scientific judgement should be exercised in deciding whether reporting is appropriate in other situations, such as important medical events that may not be immediately life-threatening or result in death or hospitalisation but may jeopardise the subject or may require medical or surgical intervention to prevent one of the other outcomes listed in the above definition. These should also be considered serious.

Examples of such events are invasive or malignant cancers, intensive treatment in an emergency room or at home for allergic bronchospasm, blood dyscrasias or convulsions that do not result in hospitalisation.

8.1.3. **Solicited adverse events**

8.1.3.1. **Solicited local (injection-site) adverse events**

The following local (injection-site) AEs will be solicited:

Table 12 Solicited local adverse events

Pain at injection site
Redness at injection site
Swelling at injection site

8.1.3.2. **Solicited general adverse events**

The following general AEs will be solicited:

Table 13 Solicited general adverse events

Fatigue
Fever
Gastrointestinal symptoms [†]
Headache
Myalgia
Shivering

[†]Gastrointestinal symptoms include nausea, vomiting, diarrhoea and/or abdominal pain.

Note: Temperature will be recorded in the evening. Should additional temperature measurements be performed at other times of day, the highest temperature will be recorded in the eCRF. The preferred route for recording temperature in this study will be oral.

8.1.4. **Clinical laboratory parameters and other abnormal assessments qualifying as adverse events or serious adverse events**

In absence of diagnosis, abnormal laboratory findings (e.g. clinical chemistry, haematology, urinalysis) or other abnormal assessments (e.g. imaging studies) that are judged by the investigator to be clinically significant will be recorded as AE or SAE if they meet the definition of an AE or SAE (refer to Sections 8.1.1 and 8.1.2). Clinically significant abnormal laboratory findings or other abnormal assessments that are present at baseline and significantly worsen following the start of the study will also be reported as AEs or SAEs.

The investigator will exercise his or her medical and scientific judgement in deciding whether an abnormal laboratory finding or other abnormal assessment is clinically significant.

8.1.5. Adverse events of specific interest**8.1.5.1. Potential immune-mediated diseases**

Potential immune-mediated diseases (pIMDs) are a subset of AEs that include autoimmune diseases and other inflammatory and/or neurologic disorders of interest which may or may not have an autoimmune aetiology. AEs that need to be recorded and reported as pIMDs include those listed in [Table 14](#).

However, the investigator will exercise his/her medical and scientific judgement in deciding whether other diseases have an autoimmune origin (i.e. pathophysiology involving systemic or organ-specific pathogenic autoantibodies) and should also be recorded as a pIMD.

Table 14 List of potential immune-mediated diseases

Neuroinflammatory disorders	Musculoskeletal disorders	Skin disorders

 • Cranial nerve disorders, including paralyses/paresis (e.g. Bell's palsy) • Optic neuritis • Multiple sclerosis • Transverse myelitis • Guillain-Barré syndrome, including Miller Fisher syndrome and other variants • Acute disseminated encephalomyelitis, including site specific variants: e.g. non-infectious encephalitis, encephalomyelitis, myelitis, myeloradiculoneuritis • Myasthenia gravis, including Lambert-Eaton myasthenic syndrome • Immune-mediated peripheral neuropathies and plexopathies, (including chronic inflammatory demyelinating polyneuropathy, multifocal motor neuropathy and polyneuropathies associated with monoclonal gammopathy). • Narcolepsy 	
 • Systemic lupus erythematosus and associated conditions • Systemic sclerosis (Systemic sclerosis), including diffuse systemic form and CREST syndrome • Idiopathic inflammatory myopathies, including dermatomyositis • Polymyositis • Antisynthetase syndrome • Rheumatoid arthritis, and associated conditions including juvenile chronic arthritis and Still's disease • Polymyalgia rheumatica • Spondyloarthritis, including ankylosing spondylitis, reactive arthritis (Reiter's Syndrome) and undifferentiated spondyloarthritis • Psoriatic arthropathy • Relapsing polychondritis • Mixed connective tissue disorder 	
 • Psoriasis • Vitiligo • Erythema nodosum • Autoimmune bullous skin diseases (including pemphigus, pemphigoid and dermatitis herpetiformis) • Alopecia areata • Lichen planus • Sweet's syndrome • Localised Scleroderma (Morphea)
Vasculitides	Blood disorders	Others

 • Large vessels vasculitis including: giant cell arteritis such as Takayasu's arteritis and temporal arteritis. • Medium sized and/or small vessels vasculitis including: polyarteritis nodosa, Kawasaki's disease, microscopic polyangiitis, Wegener's granulomatosis, Churg-Strauss syndrome (allergic granulomatous angiitis), Buerger's disease (thromboangiitis obliterans), necrotizing vasculitis and anti-neutrophil cytoplasmic antibody (ANCA) positive vasculitis (type unspecified), Henoch-Schonlein purpura, Behcet's syndrome, leukocytoclastic vasculitis. 	
 • Autoimmune hemolytic anemia • Autoimmune thrombocytopenia • Antiphospholipid syndrome • Pernicious anemia • Autoimmune aplastic anaemia • Autoimmune neutropenia • Autoimmune pancytopenia 	
 • Autoimmune glomerulonephritis (including IgA nephropathy, glomerulonephritis rapidly progressive, membranous glomerulonephritis, membranoproliferative glomerulonephritis, and mesangioproliferative glomerulonephritis) • Ocular autoimmune diseases (including autoimmune uveitis and autoimmune retinopathy) • Autoimmune myocarditis/cardiomyopathy/Sarcoidosis • Stevens-Johnson syndrome • Sjögren's syndrome • Idiopathic pulmonary fibrosis • Goodpasture syndrome • Raynaud's phenomenon

Liver disorders	Gastrointestinal disorders	Endocrine disorders

 Autoimmune hepatitis Primary biliary cirrhosis Primary sclerosing cholangitis Autoimmune cholangitis 	
 Inflammatory Bowel disease, including Crohn's disease, ulcerative colitis, microscopic colitis, ulcerative proctitis Celiac disease Autoimmune pancreatitis 	
 Autoimmune thyroiditis (including Hashimoto thyroiditis) Grave's or Basedow's disease Diabetes mellitus type I Addison's disease Polyglandular autoimmune syndrome Autoimmune hypophysitis

When there is enough evidence to make any of the above diagnoses, the AE must be reported as a pIMD. Symptoms, signs or conditions which might (or might not) represent the above diagnoses, should be recorded and reported as AEs but not as pIMDs until the final or definitive diagnosis has been determined, and alternative diagnoses have been eliminated or shown to be less likely.

In order to facilitate the documentation of pIMDs in the eCRF, a pIMD standard questionnaire and a list of preferred terms (PTs) and PT codes corresponding to the above diagnoses will be available to investigators at study start.

Once a pIMD is diagnosed (serious or non-serious) in a study subject, the investigator (or designate) must complete, date and sign an electronic Expedited Adverse Events Report.

8.2. Detecting and recording adverse events and serious adverse events

8.2.1. Time period for detecting and recording adverse events and serious adverse events (Amended 18 August 2017)

All AEs starting 30 days following administration of each dose/the dose of study vaccine (Day 0 to Day 29) must be recorded into the appropriate section of the eCRF, irrespective of intensity or whether or not they are considered vaccination-related.

All SAEs will be collected and recorded from the time of the first receipt of study vaccine at Visit 2 until the subject is discharged from the study or until the end of the study (Table 15). See Section 8.3 for instructions on reporting of SAEs.

All AEs/SAEs leading to withdrawal from the study will be collected and recorded from the time of the first study visit up to the last study visit at the end of the study.

SAEs related to initial vaccination course from study ZOSTER-003 will be collected and recorded from the time of the first study visit and will end at the time of the first receipt of dose one of re-vaccination course.

In addition to the above-mentioned reporting requirements and in order to fulfil international reporting obligations, SAEs that are related to study participation (i.e. protocol-mandated procedures, invasive tests, a change from existing therapy) or are related to a concurrent GSK medication/vaccine will be collected and recorded from the

time the subject consents to participate in the study until she/he is discharged from the study.

The time period for collecting and recording of pIMDs will begin at Visit 2, the first receipt of study vaccine and will end 365 days following administration of the last dose of study vaccine. See section [8.3](#) for instructions on reporting of pIMDs.

An overview of the protocol-required reporting periods for AEs, SAEs, IMCs and pIMDs is given in [Table 15](#).

Table 15 Reporting periods for collecting safety information

Event	Visit 1*	Visit 2			Visit 3	Visit 4			Visit 5	Contacts	Visit 6	
Timepoint	Year 9	Year 10 Vacc 1	Post Vacc	Post Vacc	Post Vacc	Vacc 2	Post- Vacc	Post Vacc				
	Month 108	Month 120	6 days post V1	29 days post V1		Month 121	Month 122	6 days post V2	29 days post V2	Month 123	Month 126, 129 and 132	Month 134
Solicited local and general AEs												
Reporting of unsolicited AE												
Reporting of any SAEs after the first dose from the re-vaccination course at Visit 2 (Amended 18 August 2017)												
Reporting of any AEs/SAEs leading to withdrawal from the study (Amended 18 August 2017)												
Reporting of all SAEs related to investigational vaccine, study participation or to a concurrent GSK medication/vaccine† (Amended 18 August 2017)												
Reporting of pIMDs												
Reporting of intercurrent medical conditions‡												

* i.e. consent obtained; Vacc 1- re-vaccination dose 1; Vacc 2- re-vaccination dose 2

† SAEs related to investigational vaccine include SAEs occurring between V1 and V2 considered as related to initial vaccination in ZOSTER-003 study and SAEs related to re-vaccination course occurring after administration of the 1st dose from re-vaccination course.

‡Including suspected cases of HZ

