3. STUDY DESIGN OVERVIEW

Figure 1 Study design overview

* Visits only performed by initial 104 subjects enrolled in Germany

** In ZOSTER-003, subjects received vaccination at Month 0 and Month 2. Months 48, 60, 72, 108 and 120 are respectively 48, 60, 72, 108 and 120 after first dose of vaccination.

Months 120, 121, 122, 123 and 134 correspond to Month 0, 1, 2, 3 and 14 of the re-vaccination course.

§ N is the number of subjects that were planned to be enrolled in ZOSTER-003

Protocol waivers or exemptions are not allowed with the exception of immediate safety concerns. Therefore, adherence to the study design requirements, including those specified in the outline of study procedures (Section 5.5), are essential and required for study conduct.

- Experimental design: Phase IIIB, open-label, multi-centric, single group.
- Duration of the study: The intended duration of the study per subject is approximately 26 months.
 - Epoch 001: Long-term follow-up starting at Visit 1 (Month 108, Year 9) and ending at Visit 6 (Month 134).
- Study group: Subjects vaccinated with 2 doses of HZ/su (group 50µg gE/AS01_B) in study ZOSTER-003 will be offered participation in this study.

Table 1 Study groups and epochs foreseen in the study

Study Groups	Number of subjects	Epochs
		Epoch 001
50µg gE/AS01 _B	~100	x

Table 2 Study groups and treatment foreseen in the study

Treatment name	Vaccine/Product name	Study Groups
HZ/su	VZV gE	50µg gE/AS01 _B
	AS01B	

- Control: Uncontrolled.
- Vaccination schedule: Visit 2 (Month 120) and Visit 4 (Month 122) in the re-vaccination phase.
- Treatment allocation: All subjects will receive HZ/su and will be assigned to the two age cohorts (60-69 years of age [YOA] and \geq 70 YOA at the time of the initial vaccination) as defined in the ZOSTER-003 study.
- Blinding: Open-label.

Table 3 Blinding of study epochs

Study Epochs	Blinding
Epoch 001	Open-label

- Sampling schedule: Blood samples for immunogenicity evaluation will be collected at the following study visits:
 - Visit 1 (Month 108/Year 9), Visit 2 (Month 120/Year 10), Visit 3 (Month 121/ one month after re-vaccination dose 1), Visit 5 (Month 123/ one month after re-vaccination dose 2) and Visit 6 (Month 134/ 12 months after re-vaccination dose 2).
- Type of study: extension of other protocols, i.e., ZOSTER-003.
- Data collection: Electronic Case Report Form (eCRF).

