5.5. Outline of study procedures

Table 4 List of study procedures

Epoch 001							
Type of contact	Visit 1	Visit 2	Visit 3	Visit 4	Visit 5	Contacts	Visit 6
Timepoints	Year 9‡ Month 108 §	Year 10‡ Month 120 #	Month 121 #	Month 122 #	Month 123 #	Month 126 Month 129 Month 132	Month 134 #
Sampling timepoints for Long-Term Follow-up Phase	Post-Vacc	Post-Vacc					
Sampling timepoints for Re-vaccination Phase		Pre-Vacc1	Post-Vacc1		Post-Vacc2		Post-Vacc2
Informed consent	●						
Check inclusion/exclusion criteria	●						
Collect demographic data	●						
Medical history	●	●					
History directed physical examination	O	O					
Check contraindications and warnings and precautions		●		●			
Pre-vaccination body temperature		●		●			
Vaccine administration		●		●			
Blood sampling for antibody determination ((5 ml))	●	● *	●		●		●
Blood sampling for CMI response ((20 ml))	●	● *	●		●		●
Record any concomitant medications/vaccinations	●	●	●	●	●	●	●
Distribution of diary cards		O		O			
Return of diary cards			O		O		
Transcribing of solicited symptoms reported within 7 days post-vaccination			●		●		
Transcribing of non-serious adverse events reported within 30 days post-vaccination			●		●		
Recording of Intercurrent Medical Conditions (IMCs)	●	●	●	●	●	●	●
Recording of any SAEs after the first dose from the re-vaccination course at Visit 2 (Amended 18 August 2017)			●	●	●	●	●
Recording of any AEs/SAEs leading to withdrawal from the study (Amended 18 August 2017)	●	●	●	●	●	●	●
Recording of SAEs related to investigational vaccine, study participation or to a concurrent GSK medication/vaccine †	●	●	●	●	●	●	●
Recording of any pIMDs		●	●	●	●	●	●
Recording of HZ cases **	●	●	●	●	●	●	●
Study Conclusion							●

Note: The double-line border following Month 108 and Month 123 indicates the analyses which will be performed on all data (i.e. data that are as clean as possible) obtained up to Month 108/123.

Vacc: vaccination

● is used to indicate a study procedure that requires documentation in the individual eCRF

O is used to indicate a study procedure that does not require documentation in the individual eCRF

§ Subjects can complete Visit 1 between 108 and 111 months after the first HZ/su dose of the previous vaccination course in ZOSTER-003.

‡ Months 108 and 120 after first dose of initial vaccination course in study ZOSTER-003

Months 120, 121, 122, 123 and 134 correspond to Month 0, 1, 2, 3 and 14 of the re-vaccination course.

* Before vaccine administration.

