6.5. Contraindications to subsequent vaccination

The following events constitute absolute contraindications to (further) administration of HZ/su. If any of these events occur during the study, the subject must not receive additional doses of vaccine but may continue other study procedures at the discretion of the investigator (see Section [8.4](#)).

- Anaphylaxis following the administration of any previous dose of HZ/su.
- An SAE judged to be related to HZ/su by the investigator.
- Active HZ infection i.e. HZ lesions not completely crusted over at the moment of Visit 2 or an episode of HZ between Visit 2 (Month 120: re-vaccination dose 1) and Visit 4 (Month 122: re-vaccination dose 2).

- Any confirmed or suspected immunosuppressive or immunodeficient condition, resulting from disease (e.g., malignancy, HIV infection) or immunosuppressive/cytotoxic therapy (e.g., medications used during cancer chemotherapy, organ transplantation or to treat autoimmune disorders). However subjects who have received less than 15 days of immunosuppressants or other immune modifying drugs should not be contraindicated from receiving subsequent vaccinations. Corticosteroids, prednisone < 20 mg/day, or equivalent, as well as inhaled and topical steroids are allowed.
- Administration of a vaccine not foreseen by the study protocol within the period starting 30 days before the first dose of study vaccine, and ending 30 days after the last dose of study vaccine. However, licensed non-replicating vaccines (i.e. inactivated and subunit vaccines, including inactivated and subunit influenza vaccines, with or without adjuvant for seasonal or pandemic flus) may be administered up to 8 days prior to dose 1 and/or dose 2 and/or at least 14 days after any dose of study vaccine.
- Administration of vaccine against HZ or varicella (including an investigational or non-registered vaccine) other than the study vaccine.
- Participating or planned participation in another clinical study, from 30 days before Visit 2 up to 30 days post second dose, in which the subject is or will be exposed to an investigational or a non-investigational vaccine/product (pharmaceutical product or device).
- Any condition that in the judgment of the investigator would make intramuscular injection unsafe.
- Other events that constitute contraindications to administration of HZ/su vaccine.

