9.2.2. Subject withdrawal from investigational vaccine

A ‘withdrawal’ from the investigational vaccine refers to any subject who does not receive the complete treatment, i.e. when no further planned dose is administered from the date of withdrawal. A subject withdrawn from the investigational vaccine may not necessarily be withdrawn from the study as further study procedures or follow-up may be performed (safety or immunogenicity) if planned in the study protocol.

All data collected until the date of withdrawal/last contact of the subject will be used for the analysis.

Information relative to premature discontinuation of the investigational vaccine will be documented on the Vaccine Administration page/screen of the eCRF. The investigator will document whether the decision to discontinue further vaccination was made by the subject himself/herself or by the investigator, as well as which of the following possible reasons was responsible for withdrawal:

- Serious adverse event.
- Non-serious adverse event.
- Other (specify).

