 - Occurrence, intensity and relationship to vaccination of unsolicited AEs during 30 days (Days 0-29) after each vaccination, according to the Medical Dictionary for Regulatory Activities (MedDRA) classification in all subjects
- SAEs
 - Occurrence and relationship to vaccination of all SAEs from dose 1 of re-vaccination until study end.
 - Occurrence of any fatal SAEs from dose 1 of re-vaccination until study end.

- Potential immune-mediated diseases (pIMDs)
 - Occurrence and relationship to vaccination of any pIMDs from dose 1 of re-vaccination until study end in all subjects.

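### Section 8.2.1 closes pIMD collection 365 days after the last dose, while the endpoint, Table 4 and Section 5.6.13 run to Visit 6

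*Protocol*

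**What the plan says.** Protocol 8.2.1 opens the window at the first re-vaccination dose: "The time period for collecting and recording of pIMDs will begin at Visit 2, the first receipt of study vaccine". The same sentence closes it: it "will end 365 days following administration of the last dose of study vaccine". In the same section, SAEs are collected from that first dose until discharge or the end of the study.

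Four other places set a different end for pIMDs:

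- The secondary endpoint in Protocol 10.2, repeated in the synopsis and in SAP 4.2, is "Occurrence and relationship to vaccination of any pIMDs from dose 1 of re-vaccination until study end in all subjects". Section 3 ends the study for a subject at Visit 6, Month 134.
- The pIMD row of Table 4 carries six marks. These fit Visit 2 through Visit 6, counting the contacts as one column.
- Section 5.6.13 lists pIMDs among the items to collect at the concluding visit and sets no day limit.
- Section 5.6.8.1 makes pIMDs one of the topics of the contacts between Visits 5 and 6.

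Subjects who do not receive dose 2 can remain under observation. Under Section 6.5, after an absolute contraindication, "the subject must not receive additional doses of vaccine but may continue other study procedures at the discretion of the investigator". Section 9.2.2 adds: "A subject withdrawn from the investigational vaccine may not necessarily be withdrawn from the study as further study procedures or follow-up may be performed".

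**The concern.** A safety endpoint should be collected over the time that it claims to cover. Under 8.2.1 the cut-off is tied to the last dose received, so it comes earliest, relative to Visit 6, for subjects who stop after dose 1. The endpoint makes no such distinction. If the last dose was meant as the planned second dose, the period has no defined end for those subjects, which also needs correcting.

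Three features give the mismatch some weight:

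- Non-serious AEs are otherwise recorded only to Day 29 after each dose, apart from events leading to withdrawal. A late non-serious pIMD therefore depends mainly on the pIMD window.
- Section 8.3.1 ties prompt reporting of pIMDs to the period defined in Section 8.2.
- Protocol 10.5.1 and SAP 7.2.2 treat a vaccinated subject without a report as event-free. An event that is not collected can therefore only lower the pIMD proportion.

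Section 1.3.1 lists pIMDs as a vaccine risk and relies on monitoring under the protocol as the mitigation, so the protocol should state one window.

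**Working it through.** **Inputs**

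| Item | Value | Source |
|---|---|---|
| Stated end of pIMD collection | 365 days after last dose | Protocol 8.2.1 |
| Visit 2 (dose 1) to Visit 4 (dose 2) | 49 to 83 days, nominal 2 months | Table 5 |
| Visit 4 to Visit 6 | 327 to 401 days, nominal 12 months | Table 5 |
| Visit 2 to Visit 6 | no window given; nominal 14 months | Table 5; Table 4 footnote |
| Planned subjects | about 100 | Table 1 |

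The nominal 14 months come from the footnote to Table 4: "Months 120, 121, 122, 123 and 134 correspond to Month 0, 1, 2, 3 and 14 of the re-vaccination course".

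**The plan's own figure.** Twelve months is 12 × 30.44 = 365 days. The 365-day limit therefore coincides with Visit 6 for a two-dose subject seen exactly on schedule.

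**Formula.** Gap = (days from last dose received to Visit 6) − 365. A negative value means that the stated period outlasts the study visit.

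**Two-dose subjects** (last dose at Visit 4)

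- Earliest Visit 6: 327 − 365 = −38 days, so no gap.
- Nominal: 365 − 365 = 0 days.
- Latest Visit 6: 401 − 365 = 36 days.

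Endpoint time is uncovered only when Visit 6 falls on days 366 to 401.

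**Subjects who receive only dose 1 and stay to Visit 6** (last dose at Visit 2, with Visit 6 assumed to keep the schedule that Visit 4 would have set)

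- Shortest: 49 + 327 = 376 days; 376 − 365 = 11 days, which is 11/376 = 3% of the time from dose 1 to Visit 6.
- Nominal: 14 × 30.44 = 426 days; 426 − 365 = 61 days, which is 61/426 = 14%.
- Longest: 83 + 401 = 484 days; 484 − 365 = 119 days, which is 119/484 = 25%.

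At nominal timing the cut-off for such a subject falls at Month 132 and Visit 6 at Month 134.

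**Which events could be missed**

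1. Serious pIMDs: collected as SAEs to discharge or study end (8.2.1), so not missed.
2. Events leading to withdrawal from the study: recorded through the last visit (8.2.1), so not missed.
3. A further pIMD in a subject already counted: Protocol 10.8.2 and SAP 6.3.2 count subjects, so the overall count does not change. It could change a preferred-term row.
4. A first, non-serious pIMD with onset in the gap: outside the period in 8.2.1. This is the exposure.

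**Scale.** One such subject among about 100 moves the proportion by 1/100, or about one percentage point. The number of one-dose subjects is not given.

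**The case against.** The strongest reply is that the working instructions already run to Visit 6. Table 4, Section 5.6.8.1 and Section 5.6.13 all have sites ask about pIMDs up to the end, and a site that follows them would capture late events. The gaps above arise only where the sentence in 8.2.1 is applied over those instructions. This stands, and it means that the defect is a contradiction rather than a demonstrated loss of data. It does not remove the problem, because ascertainment would then depend on which section a site follows.

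A reader might infer that under-reporting is worst among subjects taken off vaccine for safety, since a new or worsening pIMD or a related SAE can stop dose 2. The documents do not support this for pIMDs. A subject refused dose 2 because of a pIMD after dose 1 had that event inside the window and is already counted, and Section 8.4 has it followed further. What remains is a subject stopped for another reason who then has a first, non-serious pIMD late.

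Two further points stand. For two-dose subjects the gap is nil at nominal timing, and 36 days is the edge of the window. The range of 11 to 119 days combines extremes of two windows and assumes that Visit 6 stays anchored to a Visit 4 at which no dose was given. The period bars of Table 15 are not readable in the text available, so that table cannot settle the matter either way.

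**Conclusion.** The inconsistency is real and is in the current text: one sentence in 8.2.1 disagrees with the endpoint, Table 4 and Section 5.6.13. Its size is modest and conditional on a site applying 8.2.1:

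- two-dose subjects: none when Visit 6 falls by day 365, at most 36 days within the window;
- one-dose subjects who stay to Visit 6: about 61 days at nominal timing, 11 to 119 days under the anchoring assumption.

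The Table 5 intervals are not firm limits, so a later visit would widen the gap. A one-dose subject who leaves by day 365 has none. Any bias is downward and confined to first, non-serious pIMDs in the gap, so with about 100 subjects it is probably small. The documents do not show that pIMDs go uncollected, nor that the loss falls mainly on subjects withdrawn from vaccine for safety. The point is worth correcting because a stated collection rule should match the safety endpoint that it serves.

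**What to change.** Reconcile Section 8.2.1 with the endpoint. State that pIMDs are collected from the first re-vaccination dose at Visit 2 until Visit 6 or discharge from the study, for every vaccinated subject, whatever number of doses was received. This is the rule that 8.2.1 already uses for SAEs, and it brings each gap above to 0 days. Check that the pIMD row of Table 15 shows the same period. Table 4, Section 5.6.13 and the endpoint text in Protocol 10.2 and SAP 4.2 need no change.

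The cost is an edit to the protocol wording, with no new visit or procedure. Some subjects would have a few more weeks of pIMD reporting. For two-dose subjects seen on days 327 to 364, the period would end at Visit 6 instead of up to 38 days after it (365 − 327), a time in which no visit or contact is scheduled.
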